## 1.0 Objectives

### 1.1 Study Objectives

**AIM 1.** To compare the effectiveness of exercise coaching with enhanced usual care in reducing serious fall-related injuries (SFRI), including fragility fractures from a fall, among older adults with a prior fragility fracture. We hypothesize that 13% of control subjects will experience a SFRI versus 7% of exercise subjects after the 36 months.

**AIM 2.** To compare the effectiveness of exercise coaching versus enhanced usual care on other patient-centered outcomes (total number of falls, loneliness, physical function, muscle strength, bone density, and muscle mass) that patients told us they were interested in. We hypothesize that exercise coaching will significantly improve each of these outcomes.

**AIM 3.** To examine heterogeneity of treatment effects (HT-1) with regard to key participant factors (age, gender, race, ethnicity, osteoporosis medication use, intervention engagement, patient choice of exercise location – in-home v. community). We hypothesize that sub-groups can be identified for whom a particular intervention approach is most effective, to help inform patient-, provider- and key stakeholder decision makers. Of note, many of these subgroup analyses are not fully powered, particularly given the reduction in sample size from the original 2100 to the modified 1130. There is, as a result, less than 80% power to detect significant differences for most of these subgroup analyses. These analyses will, however, suggest where differences lie that can be further evaluated in future studies.

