### **7.2.6.3. Randomization**

Once eligible participants who sign the informed consent and completed the baseline questions, research staff at each site will randomize the participant into one of two groups (control, enhanced usual care; or intervention groups, enhanced usual care plus coached exercise program) in a one-to-one ratio. Stratification factors for randomization will be study site location (1=Penn State, 2=University of Pittsburgh, 3=Temple University), gender (0=female, 1=male), and bisphosphonate and other potent medication use (0=never, 1=ever). The research staff will conduct the randomization during the baseline visit through REDCap.

Participants randomized to the intervention group will also receive an introductory letter from their exercise coach with picture/name and details on a forthcoming phone call.

Group leaders, community members, and Spanish Speaking Interview members will not be randomized.

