### **Exercise program at home and/or community sites**

Our study design is to be "pragmatic", therefore, the intervention is designed to be something that the vast majority of people would be interested in, and we know that some people are shy and avoid group programs or do not like to travel. For that reason we have created an "at home" option, which will include the same exercises at the same times, but via DVD. Participants who regularly attend class, but may miss a session due to vacation or other obligations and insist on doing the exercises remotely, may be given the home exercise manual if they don't have

access to a DVD player. The home exercise manual can be used as a reminder for the proper way to perform the exercises that they have already learned and reviewed with their exercise coach. The manual is not intended to replace the Band Together sessions or Band Together DVD. This allows “choice” to be part of the study, though it will be a limitation as well. Giving people options is important and is part of standard clinical care, which this study – a pragmatic clinical trial – is designed to approximate.

Patients will have the choice to participate at home and/or at community sites and can modify that ratio as they choose. As a key secondary outcome is loneliness, the coach will encourage participation at community sites, but patients will choose.

The “at home” option for the exercise session will also be heavily utilized during times that our in-person community exercise sessions may be canceled due to circumstances outside of the study’s control. These circumstances may include weather related cancellations, disease outbreaks and/or recommendations from Penn State University or Milton S. Hershey Medical Center to stop in-person visits. When these circumstances arise, we will contact intervention participants and encourage them to participate in the DVD portion of the program. Exercise Coaches will continue to make contact with the research participants during these cancellations to ensure exercise are being done properly and to collect adverse events, as needed.

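### Aim 3 lists engagement and exercise location as effect modifiers, but both arise after randomisation and only in the exercise arm, so no interaction can be estimated and any contrast with controls is non-randomised

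*Combined protocol and SAP*

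**What the plan says.** Section 1.1 states the purpose of Aim 3: "To examine heterogeneity of treatment effects (HT-1) with regard to key participant factors". Seven factors follow. Age, gender, race and ethnicity come first, then "osteoporosis medication use, intervention engagement, patient choice of exercise location – in-home v. community". The aim concedes "less than 80% power to detect significant differences for most of these subgroup analyses" and describes the results as leads: "These analyses will, however, suggest where differences lie that can be further evaluated in future studies".

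Other sections show when the last two factors come into being:

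- **Randomisation** (section 7.2.6.3): "The research staff will conduct the randomization during the baseline visit through REDCap". The strata are site, gender and bisphosphonate or other potent medication use. Location preference is not a stratum, and no section describes asking for it before allocation.
- **Controls** (section 7.2.6.3, Group A) are encouraged to exercise but have no access to the study programme or its coaches.
- **Engagement** (Regular Progress Reports): the coach records adherence every month during the intervention.
- **Location** (Exercise program at home and/or community sites): "Patients will have the choice to participate at home and/or at community sites and can modify that ratio as they choose". Site closures also shift people to home exercise: "When these circumstances arise, we will contact intervention participants and encourage them to participate in the DVD portion of the program".

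Section 8.3 specifies intention to treat with covariates for the primary outcome. It gives no model for Aim 3, no definition of engagement or of a location group, and no comparator for either.

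**The concern.** A factor can modify a treatment effect in a randomised comparison only if it is defined in both arms and is not itself a result of allocation. Age and gender qualify. Engagement with the programme and place of exercise do not, because a control participant has no value for either.

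What remains as an effect estimate is a part of the exercise arm, sorted by behaviour after allocation, set against controls who were not sorted. Two mechanisms can then produce a difference without any treatment effect. People who attend well may have had a lower risk from the start. A serious fall may itself reduce attendance: section 3.3.1 allows withdrawal of injured participants, and section 7.2.6.3 (Group B) sets a review before return after hospitalisation or a long absence.

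Aim 3 is meant to help patients, providers and other decision makers see for whom the programme works. A pattern created by selection would mislead them, and a larger later study repeating the same contrast would reproduce it.

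**Working it through.** **1. The plan's own figure.** Inputs from section 8.3: 13% v 7%, 960 remaining (480 per arm), two-sided 5%.

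- SE under the null = √(2 × 0.10 × 0.90 / 480) = 0.01936.
- SE under the alternative = √((0.13 × 0.87 + 0.07 × 0.93) / 480) = 0.01927.
- Power = Φ((0.06 − 1.96 × 0.01936) / 0.01927) = Φ(1.14) = 87%, as stated.
- 960 / 0.85 = 1130, as stated.

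The point does not depend on these figures, but they supply the event count in step 5.

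**2. Estimability.** An interaction compares exercise with control at each level of a factor. For age that needs four cells (two arms by two levels), and all four exist. For engagement or location the two control cells are empty, so the interaction is not defined.

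**3. Bias from selection alone, with no treatment effect.** Risk is 13% in both arms. Assume that a share q of the exercise arm is engaged and has g times the risk of the non-engaged (q and g are assumptions). Then non-engaged risk = 0.13 / (qg + 1 − q), and engaged risk = g times that.

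| q | g | Engaged RR v control | Non-engaged RR v control |
|---|---|---|---|
| 0.5 | 1.0 | 1.00 | 1.00 |
| 0.5 | 0.8 | 0.116/0.13 = 0.89 | 0.144/0.13 = 1.11 |
| 0.5 | 0.5 | 0.087/0.13 = 0.67 | 0.173/0.13 = 1.33 |
| 0.5 | 1.25 | 0.144/0.13 = 1.11 | 0.116/0.13 = 0.89 |

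Over q = 0.3 to 0.7 and g = 0.5 to 0.8, the engaged RR runs from 0.59 to 0.93 and the non-engaged RR from 1.06 to 1.54. The share-weighted risk is 13% in every case. With q = 0.5, a test of engaged against all controls falsely shows benefit 7.6% of the time at g = 0.8 and 39.7% at g = 0.5, against a nominal 2.5%.

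**4. Adding lost attendance, with no treatment effect.** Assumptions: engaged means at least 50% of sessions; 30% of participants are frail, with 2.5 times the hazard and mean attendance of 45% v 60%; six months of attendance are lost after a serious fall; attendance is beta-distributed. By simulation, the engaged RR is 0.49 if the SD of attendance is 0.10, 0.68 at 0.20 and 0.85 at 0.35. The documents give no SD, so only the range can be reported. For scale, the hypothesised true ratio is 7/13 = 0.54.

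**5. Interaction power for a valid baseline factor, SFRI only.** Events = 480 × (0.13 + 0.07) = 96. Hazard ratio = ln 0.93 / ln 0.87 = 0.521. Take the full effect in one subgroup, none in the other, and a fraction f of events in the first. Then SE = √(4/(Df) + 4/(D(1 − f))) and power = Φ(ln(1/0.521)/SE − 1.96).

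- D = 96, 50/50: SE = 0.408, power 36%.
- D = 96, 80/20: SE = 0.510, power 25%.
- D = 96, 90/10: SE = 0.680, power 16%.
- If half the trial has no effect, events rise to 240 × 0.20 + 240 × 0.26 = 110, and power at 50/50 is 40%.

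**The case against.** The best defence is that Aim 3 is openly exploratory. It admits low power, defers to future studies, and the home-exercise section itself calls choice a limitation. The plan names no comparator, so it never commits to setting engaged participants against controls. A within-arm description would be compatible with its text. The primary analysis is intention to treat and is not touched.

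Much of this stands, and it lowers the severity. It does not remove the point. Low power concerns imprecision, whereas this is bias, and neither caveat says that these two factors lie outside the randomised comparison. The aim calls them factors for heterogeneity of treatment effect, which is what they cannot be.

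Three stronger readings are tempting, and the documents do not support them:

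- *These subgroups will favour exercise even with no effect.* Step 3 shows opposite directions for engaged and non-engaged, a reversal if g exceeds 1, and no bias if the factor is unrelated to risk. For location, nothing in the documents indicates a direction.
- *The trial will report that the engaged benefit and the rest do not.* That presumes a comparator which the plan does not name. It also presumes that injury always stops attendance, whereas the protocol makes withdrawal only possible and provides a route back and a home option.
- *No interaction test reaches 80% power.* Aim 3 names no outcome. For SFRI with D = 96 and a 50/50 split, 80% is reached at a ratio of hazard ratios of exp(2.80 × 0.408) ≈ 3.1. For a continuous Aim 2 outcome with 240 in each of four cells, it is reached at 2.80 × √(4/240) = 0.36 SD. The plan's wording, that most analyses fall short, can stay.

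**Conclusion.** Wrong as written, and it should be fixed. For two of the seven Aim 3 factors the stated target, heterogeneity of treatment effect, cannot be estimated: the factors arise after allocation and are undefined in controls. That conclusion needs no assumption beyond the protocol's text. Any comparison of such a subset with controls is observational.

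The direction and size of the bias do rest on assumptions. If engagement is related to lower risk, or injury reduces attendance, the engaged subset tends to look better than controls and the non-engaged worse under no effect. Under the step 4 assumptions the engaged risk ratio is 0.49 to 0.85 when the truth is 1. For location no direction can be given. The primary result is not at risk.

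**What to change.** 1. Limit the Aim 3 heterogeneity analysis to age, gender, race, ethnicity and osteoporosis medication use, each tested by a treatment-by-factor interaction. State that medication use means the baseline value, since section 1.3 also collects a medication list at 36 months.
2. Remove engagement and location from the list of effect modifiers. Report both as descriptive, non-randomised summaries within the exercise arm, with no claim of effect against controls.
3. A complier-average effect for engagement may be added as a sensitivity analysis only. It needs an engagement threshold fixed in advance, and the exclusion restriction (no effect of assignment on those who do not engage) stated as an assumption. That assumption is open to doubt here, because coaches call participants regularly, including after missed classes, and send progress reports to primary care providers.
4. Leave the existing power caveat as it is. If a figure is added, confine it to SFRI: about 36% to 40% with 96 to 110 events, full effect in one half and none in the other, and lower for unequal splits.
5. If the size of the bias is illustrated, show it as a range over the assumed spread of attendance.

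The cost is a change of wording in Aim 3 and a short addition to section 8.3, made before outcome data are examined by arm. No new data are needed.

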### 1.2 Primary Study Endpoints

#### **Serious Fall-Related Injuries (SFRI), including Fragility Fractures from a fall**

To identify our main outcome (SFRI, including FF), we will collect main outcome data every 4 months and during the assessment (12, 24, 36 months) using a fall calendar to record all fall events (e.g., date, location). This will help participants to recall falls during the 4 month period. Subjects will be asked, for example, *“Have you fallen in the past 4 months (or since last contact)? Were you injured in any fall in the past 4 months (or since last contact)?” “Did you land on the floor, ground or other lower level when you fell?” “When you fell, did you break or fracture a bone? or “Were you told by a doctor, or other health professional”*. For any new events, the circumstances regarding the incident (i.e., what occurred) will be recorded for use in adjudicating whether the injury was related to a FF (i.e., “low-trauma” or fall from standing height or less). The dates of injuries and the name of the institution will be recorded, so that medical records can be sought using the authorization form signed by all patients at baseline.

For any SFRI (including FF) or hospitalization/ED visits noted quarterly or during the 12, 24 or 36 months assessment, medical records will be obtained, including outpatient notes, emergency department notes, hospital discharge summary reports and radiologic notes. All outcomes (e.g., SFRI) require evidence from medical records to be counted.

These records will be collected and presented, blinded to treatment condition, 14 days before the monthly meeting to the Outcomes Committee ([name]-Chair, [name], [name], [name], [name]). For each event, the Outcomes Committee will be charged with determining whether it was 1) a fracture related to a fall from standing height or less, 2) a non-traumatic fracture not related to a fall, 3) a serious fall related injury without a fracture, 4) a traumatic fracture (e.g., MVA), 5) a non-serious fall related injury, or 6) none. A vote is made for each event. If there is not agreement, it will be opened for discussion and another vote. If

consensus is not possible, the case will be presented to [name] [name] for final adjudication, given her vast experience with this process (34, 77, 78).

We will additionally request permission from subjects to access their claims through RESDAC or a similar company and PaTH network. This will allow for comprehensive collection of data for our primary outcome. We will need the participant's health insurance claim (HIC) number for RESDAC.

### 1.3 Secondary Study Endpoints

**Self-Reported Falls and Fall-Related Injuries:** We will examine the number of falls, and fall-related injuries using two questions from the Behavioral Risk Factor Surveillance System (BRFSS) at baseline, and using the STRIDE questionnaire for all 4-month follow-up assessments (34).

**Self-Reported Health, Physical Function, Fatigue, Pain, Sleep Disturbance, Ability to Participate in Social Roles and Activities, Depression, Anxiety, Loneliness:** We will use 33 self-reported questions to assess key patient centered outcomes that the intervention may improve: self-reported health (1 question), depression (4 questions), anxiety (4 questions), physical function (4 questions), ability to participate in social roles and activities (4 questions), fatigue (4 questions), pain (5 questions), sleep disturbance (4 questions), ability to participate in social roles and activities and loneliness (3 questions). We will use depression, anxiety, fatigue, pain, sleep disturbance and physical function scales from the NIH-supported Patient Reported Outcomes Measurement Information System (PROMIS). We will also use the single-item measure of self-reported health, which is strongly predictive of many health outcomes (37, 38). We will use a 3-item loneliness questionnaire which has high 12-month test-retest reliability ( $r = 0.73$ )(39) and is predictive of future functional decline and death (40). To assess physical function, we will use the 4-item PROMIS measure of physical functioning that includes ability to *walk, do chores, run errands* and *go up and down stairs*, key physical functions. [name], a clinical psychologist and Professor at Penn State with experience in clinical trials to improve anxiety and depression (41-44), will oversee the analysis of these survey results.

**Body composition: Bone Mass, Muscle Mass, Bone architecture:** Body composition will be determined by dual energy X-ray absorptiometry (DXA) as done in routine clinical care and overseen across sites by the Body Composition Core (BCC) chaired by [name], who has decades of experience with these measures (35, 36). Measurements are taken with the subject in a supine position. Scans will be analyzed using the adult medium mode for all subjects. Phantom calibration will be performed before each scan. For densitometry, bone mineral content (BMC, g) and bone area (BA, cm^2) are measured for the total body, lumbar spine (L1–L4), and total hip (sum of the average femur neck, trochanteric region and proximal femoral shaft from dual-sided measurements). BMD (g m^2) is calculated from the BMC and BA. Total body soft tissues in terms of muscle (lean) mass and fat mass are also measured for total and regional body composition (35, 36). A major effort of the BCC will be to assure data comparability by site and to quickly create the reports for PCPs.

**Sociodemographics and Medical History:** We will measure age, gender, race and ethnicity, smoking status, education and the prevalence of common chronic conditions (i.e., osteoarthritis, osteoporosis) using questions from the Behavioral Risk Factor Surveillance System (BRFSS)(46-49).

**Blood Pressure and Heart Rate:** Blood pressure and heart rate will be measured by the study research coordinator.

**Height and weight:**

For Group leaders we will collect self-reported height and weight. These will be collected during baseline and at 36 months assessments.

For participants we will use height and weight to calculate Body Mass Index (BMI) using standardized procedures. We will use a portable, calibrated stadiometer and scale with high reliability ( $r = 0.96$ ) (50) as in [name] ongoing study.

**Fear of Falling:** We hypothesize that the intervention will reduce fear of falling as a mediator to increasing physical activity. We will use the 7-item version of the Falls Efficacy Scale International (FES-I), which has high test-retest ( $r = 0.80$ ) reliability and is strongly associated with future falls and depression ( $p < .001$ ) (51).

**Osteoporosis and Other Medications:** At baseline, past osteoporosis medication use will be obtained and, at the 36 month assessments, patients will be asked for their current list of medications.

**30 Second Chair Stand Test:** At baseline and the 36 month follow-up the participants will perform the 30 second chair stand test. This will be used as a measure of functional lower extremity strength.

**30 Second Arm Curl Test:** At baseline and the 36 month follow-up the participants will perform the 30 second arm curl test. This will be used as a measure of functional upper extremity strength.

**Cognition Screener:** Six-item Callahan screener

**Physical Activity Survey:** We will use the NHIS physical activity questions (6 questions) at baseline and 12, 24, and 36 month follow-ups to measure participants' activity level. The survey identifies patients that are sedentary, moderately active, or very active.

**Social domain – caregiver:** We will use two questions from the AARP Caregiver Identification Study, February 2001 at baseline and 36-month follow-up. We will be able to identify whether the patient is a caregiver or not.

**Additional self-reported questions:** We will have participants answer the following 16 questions on chronic conditions, recent healthcare utilization, medical devices, hospital admissions, transportation, health insurance, home care, and nursing home/rehab facility stay.

**Virtual Short Physical Performance Battery (VSPPB):** The vSPPB is a novel self-report measure that uses computer animation to present the physical tasks in the SPPB. We will send 12 questions via email at the Month 36 Visit to all participants with an email address.

## 2.0 Background

### 2.1 Scientific Background and Gaps

Fall-related fractures due to osteoporosis are a leading cause of death and disability. Fragility fracture (FF), typically fractures due to falls of standing height or less in adults with osteoporosis, are a devastating consequence of aging. Scientific advances have greatly increased lifespan and reduced the need for physical activity, producing seniors with less bone and muscle than ever before. Nearly half of women suffer a FF over their lifetime and there are approximately 1.8 million FF each year, including

300,000 hip fractures (1). Hip fractures increase the risk of death 6-fold over 3 months (2), lead to 140,000 nursing home admissions per year (3) and leave 60% unable to ever walk 10 feet without assistance (4). This matters because seniors are far more fearful of losing their independence even than dying (5).

The declining use of bisphosphonates, a key treatment for preventing FF, suggests that new options are needed. Between 2007 and 2012, the number of prescriptions filled for bisphosphonates fell by 50% (6), despite the 2008 expiration of the patent for Fosamax (alendronate). A key reason for decreasing use of these medications is their common (e.g., GI upset) and rare (e.g., osteonecrosis of the jaw) adverse effects (7). Though newer treatments exist, most are expensive and, in the case of Forteo (teriparatide), carry a black box warning about osteosarcoma risk (8). In all, this suggests that patients and providers need new treatment options to reduce the risk of FF.

Exercise programs with coaching appear to reduce FF, however, no large-scale effectiveness studies exist (RQ-1). This type of coaching support is not reimbursed by insurance today, even in programs like Silver Sneakers (11-15). Only a large-scale pragmatic trial, such as proposed, can answer the key question to inform coverage decisions: “If a doctor recommended a coach-supported exercise program, would it reduce fractures and fall-related injuries?”

Coaching interventions are effective and growing, but have not been tested to reduce fractures. Due to the ACA, the market for care management is expected to grow from \$8.3 to \$26.4 billion by 2018 (117). While care management companies offer telephone lifestyle counseling, none offer what is proposed here. Interviews with FF patients for this proposal, however, suggest that patients and their caregivers: “It would be nice to have that person once a week come over, make a little report and tell her her progress. It was such a help at that time...” and “I would want help explaining the exercises to me, because I’m afraid of falling.” If this study proves effective, Health Dialog (Project Partner) has agreed to consider offering it as a new service, and we have activities planned to encourage other care management companies to do the same.

